12.2 Trial Design, Sample Size, and Study Duration

12.2.1 Trial Design: We will use a time to event continual reassessment method (TITE-CRM) trial design [11] to enroll a maximum of 30 patients onto this protocol.

The primary goal of this trial will be to determine the SBRT dose associated with a dose-limiting toxicity (DLT) in 20% of patients. DLT will be defined as grade ≥ 3 gastrointestinal toxicity (defined further below).

The TITE-CRM extends the original CRM by weighting each patient's contribution to the likelihood function described below. To determine the recommended dose for a newly enrolled patient, model parameters are estimated via the weighted likelihood. All previously enrolled patients who had either experienced toxicity or had completed the 12-month observation period without toxicity are assigned weights of 1; otherwise they are assigned weights equal to the proportion of the observation period they have completed.

The first patient in this study will enroll at dose level #2. Dose de-escalation can occur at anytime, though dose escalation will be restricted to 1 level between sequential patients. Additionally, before escalating the dose to the next level two conditions must be met: 1) the sum of the observation periods for all patients at the current dose level must be at least 12 months; and 2) at least one patient must have been under observation for at least 6 month at the current dose level. The rationale for these two conditions is mainly due to the short life expectancy of this patient population, which has a median survival of 8.25 months.

A two-parameter logistic regression model will be used to estimate the probability of toxicity at each dose level after each patient has been enrolled, which will inform the decision as to whether we should dose-escalate the patient in question. A final two-parameter logistic model will be fitted using follow-up data from 6 months after accrual of the last patient

Table 3. A priori toxicity estimation

Dose level	Probability of dose limiting toxicity
1	0.01
2	0.05
3	0.10
4	0.20
5	0.30

12.2.2 Dose Limiting Toxicity: The only toxicity observed thus far in pancreas SBRT has been related to nearby normal gastrointestinal organs, namely the duodenum and

stomach. Dose limiting toxicity in this study will be defined as any grade 3-5 gastrointestinal toxicity as measured by the Common Terminology for Adverse Events, version 4.0 (see appendix).

12.2.3 Maximum Sample Size: 30

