12.2.4 Study duration: We anticipate accruing 12 patients per year, and will follow the last patient for a minimum of 6 months.

12.2.5 Interim analysis: This TITE-CRM trial design will de-escalate the radiation dose rapidly according to the observed dose-limiting toxicity. In addition to this built-in dose de-escalation we plan to conduct interim safety analysis after enrollment of every patient. We will stop the trial early if either of the following three conditions are met:

Condition 1 for early trial stoppage: more than 50% of patients at any dose level experience a dose-limiting toxicity.

Condition 2 for early trial stoppage: more than 34% of patients at dose level #1 experience a dose-limiting toxicity.

12.2.6 Operating Characteristics of the design: We used simulation to investigate the operating characteristics of our TITE-CRM configuration. We set the prior probability of toxicity at dose levels as in the table above, and investigate four different scenarios for the true underlying probabilities of toxicity:

- Scenario 1: Toxicity probabilities (.01, .05, .10, .20, .30) for dose 1-5, respectively (Prior Probability = True Probability)
- Scenario 2: Toxicity probabilities (.01, .05, .07, .10, .15) for dose 1-5, respectively (Prior Probability > True Probability)
- Scenario 3: Toxicity probabilities (.01, .05, .07, .10, .25) for dose 1-5, respectively (Prior Probability > True Probability)
- Scenario 4: Toxicity probabilities (.05, .10, .20, .30, .50) for dose 1-5, respectively (Prior Probability < True Probability)

We set our target rate of toxicity at the MTD to be .20, and set a vague normal prior with mean 0 and variance 1.34 (9). When a simulated patient enters the study, they are assigned to the dose chosen by the 'titecrm' function in the R library **dfcrm** (10), following the rules for dose escalation above. The incoming patient experiences a toxicity with probability given by the true underlying rate of toxicity for their assigned dose level, with toxicity time occurring uniformly between 0 and 12 months. Potential drop out (i.e. death) times are drawn randomly (with replacement) from the literature [5]. We set the number of simulations for each scenario at 5000.

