Operating characteristics of the TITE-CRM simulation under different scenarios are included in the table below. 'Power' is defined as the simulated probability that the algorithm will recommend the correct MTD, defined in our simulation as the dose whose true toxicity probability is closest to, but not greater than, the target (dose 4, 5, 4, and 3 for each of the four scenarios, respectively) at the trials conclusion. Trial duration is the amount of time (in months) from the first patients' enrollment to the end of the final patients observation period. Total Obs. is the cumulative observation time (in months) on all 30 patients. Pr(Tox.) is the simulated probability of toxicity in that configuration, and Pr(Tox. Above MTD) is the simulated probability of a subject having toxicity at a dose above the MTD.

Table 4. Operating characteristics

[figure not shown]
	‘Power’	Trial Duration	Total Obs.	Time	Pr(Tox.)	Pr(Tox. Above MTD)
Scenario 1	0.341	39.4	237.0		0.091	0.016
Scenario 2	0.436	39.4	240.5		0.062	0.014
Scenario 3	0.369	39.5	239.1		0.071	0.022
Scenario 4	0.334	39.5	233.9		0.116	0.029

The probability of recommending each dose as the MTD by scenario is included in the table below.

[figure not shown]
Table 5. Probability of recommending each dose as the MTD

	Dose 1	Dose 2	Dose 3	Dose 4	Dose 5	MTD and (MTD - 1)
Scenario 1	0.000	0.123	0.386	0.341	0.150	0.727
Scenario 2	0.001	0.068	0.195	0.299	0.436	0.736
Scenario 3	0.003	0.069	0.204	0.369	0.356	0.573
Scenario 4	0.062	0.500	0.334	0.094	0.011	0.834

A boxplot of the number of patients treated above the MTD (treated above dose 4, 4, and 3, respectively) in scenarios 1, 3 and 4 is below.

A barplot of the average number of patients treated at each dose level with each scenario is below.

REFERENCES

1. Siegel R, Naishadham D Jemal A. Cancer statistics, 2013. *CA Cancer J Clin* 2013;63:11-30.

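### Section 12.2.6 has no rule for a DLT drawn after death, and Tables 4 and 5 do not fit one common run; the stated chance of naming a level above the MTD depends on which handling was used

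*Combined protocol and SAP*

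**What the plan says.** Section 12.2.6 builds each simulated patient from two separate draws. For toxicity: "The incoming patient experiences a toxicity with probability given by the true underlying rate of toxicity for their assigned dose level", with the DLT time uniform over the 12-month window. For death: "Potential drop out (i.e. death) times are drawn randomly (with replacement) from the literature [5", that is, from the SBRT series listed as reference 5, whose individual times the protocol does not give. The section does not say what happens when the DLT time falls after the death time.

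Section 12.2.1 gives weight 1 to a patient with a DLT or with a completed DLT-free window; for the rest, "otherwise they are assigned weights equal to the proportion of the observation period they have completed". I read this as freezing a DLT-free patient's weight at death. The same section cites a median survival of 8.25 months and aims for the dose with a DLT in 20% of patients. Section 12.2.6 repeats the target: "We set our target rate of toxicity at the MTD to be .20".

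Table 4 gives Pr(Tox.) as .091/.062/.071/.116 in Scenarios 1 to 4. Table 5 gives the "probability of recommending each dose as the MTD". The correct MTD is taken as dose 4, 5, 4 and 3 respectively.

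**The concern.** Median survival is shorter than the observation window, so many simulated patients die inside it. If every drawn DLT counts but a DLT-free patient counts only up to death, the model sees too high a risk and settles on lower levels. Table 5 shows that pattern. In Scenario 1 dose 3 is chosen more often than the MTD, dose 4 (0.386 v 0.341). In Scenario 4 dose 2 is chosen more often than dose 3 (0.500 v 0.334), although dose 3 has a true rate of exactly .20.

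The selected dose goes on to a phase II trial (Section 1.4), and Table 5 is the plan's evidence on how often that dose would be too high. A patient who has died cannot have a DLT in the real trial, so the figures must rest on a stated treatment of death.

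**Working it through.** **1. The plan's figures.** Chance of naming a level above the MTD, summed from Table 5: Scenario 1, dose 5 = 0.150; Scenario 3, dose 5 = 0.356; Scenario 4, doses 4 and 5 = 0.094 + 0.011 = 0.105. Scenario 2 has its MTD at dose 5, so there is no level above it.

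**2. Direction of the effect.** Table 4 gives 237.0 months of observation in Scenario 1: 237.0/30 = 7.9 months per patient, and 7.9/12 = 0.66 of the window. If all DLTs count and DLT-free patients count 0.66 on average, a true rate p looks like p/(p + (1 - p) x 0.66):

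- p = 0.20: 0.20/(0.20 + 0.528) = 0.27
- p = 0.10: 0.10/(0.10 + 0.594) = 0.14

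In Scenario 4, dose 2 (about 0.14) then looks slightly nearer to 0.20 than dose 3 (about 0.27), as in Table 5.

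**3. Rebuilding the simulation.** From the documents: the Table 3 prior rates, normal prior with mean 0 and variance 1.34, target .20, start at level 2, one-level escalation with the 12-patient-month and 6-month conditions, 30 patients, 12 per year, uniform DLT times. Assumed: Weibull death times with median 8.25-10 months and several shapes, fixed or Poisson accrual, a one-parameter power or logistic model, choice of the level estimated closest to .20, and a final fit on full 12-month windows. Each variant was run with post-death DLTs kept and with them dropped. One pair (power model, shape 2, median 8.25, monthly accrual, 1500 trials per scenario):

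| Scenario | Source | Dose 1 | Dose 2 | Dose 3 | Dose 4 | Dose 5 |
|---|---|---|---|---|---|---|
| 1 | Table 5 | .000 | .123 | .386 | .341 | .150 |
| 1 | kept | .004 | .114 | .419 | .355 | .108 |
| 1 | dropped | .001 | .036 | .230 | .424 | .309 |
| 2 | Table 5 | .001 | .068 | .195 | .299 | .436 |
| 2 | kept | .002 | .045 | .192 | .353 | .408 |
| 2 | dropped | 0 | .023 | .104 | .264 | .609 |
| 3 | Table 5 | .003 | .069 | .204 | .369 | .356 |
| 3 | kept | .001 | .067 | .212 | .420 | .300 |
| 3 | dropped | 0 | .015 | .101 | .352 | .533 |
| 4 | Table 5 | .062 | .500 | .334 | .094 | .011 |
| 4 | kept | .111 | .453 | .362 | .073 | .001 |
| 4 | dropped | .029 | .245 | .399 | .273 | .055 |

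Summed absolute differences from Table 5 over the 20 cells are 0.48 (kept) and 1.76 (dropped). The mean total-variation distance per scenario is half of that divided by 4: 0.48/8 = 0.06 and 1.76/8 = 0.22. Across the variants under the stated rules it was 0.04-0.07 (kept) and about 0.22-0.26 (dropped). Monte Carlo error is small by comparison: for a proportion of 0.31, sqrt(0.31 x 0.69/1500) = 0.012.

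**4. Size, if post-death DLTs are dropped.** Range over the variants, against Table 5:

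| Scenario | Table 5, above MTD | Dropped | Ratio |
|---|---|---|---|
| 1 | 0.150 | 0.30-0.38 | 2.0-2.5 |
| 3 | 0.356 | 0.52-0.61 | 1.5-1.7 |
| 4 | 0.105 | 0.30-0.34 | 2.9-3.2 |

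In the tabulated run, the 'Power' column would move from 0.341 to 0.42, 0.436 to 0.61, 0.369 to 0.35 and 0.334 to 0.40: up in Scenarios 1, 2 and 4, slightly down in Scenario 3.

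**5. Table 4 points the other way.** Pr(Tox.) in the same pair of runs:

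| Scenario | Table 4 | Kept | Dropped |
|---|---|---|---|
| 1 | .091 | .121 | .091 |
| 2 | .062 | .081 | .057 |
| 3 | .071 | .094 | .070 |
| 4 | .116 | .157 | .122 |

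Table 4 divided by the kept run is .091/.121 = 0.75, .062/.081 = 0.77, .071/.094 = 0.76 and .116/.157 = 0.74, so Table 4 is about a quarter lower. One possible explanation is that all DLTs drove the dose-finding while Table 4 tallied only those before death. A run of that kind gave .087/.057/.067/.113. This is suggestive, not proof.

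**6. A separate slip.** Table 4 gives Scenario 2 a Pr(Tox. Above MTD) of 0.014. Its MTD is the top level, so this must be zero.

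**The case against.** The strongest reply concerns the scale of the rates. Section 12.2.1 speaks of a DLT in 20% of patients. If the scenario rates are crude proportions, already allowing for death, then generating DLTs at the full rate is correct and Table 5 can stand. If they are net rates and post-death DLTs are dropped, about 0.66-0.69 of drawn DLTs occur. The crude incidence at the level just above the MTD is then 0.30 x 0.66-0.69 = 0.20-0.21 (Scenarios 1 and 4) and 0.25 x 0.66-0.69 = about 0.17 (Scenario 3), at or near the 20% target. This stands: a reader might infer that the trial will often pick a too-toxic dose, and the documents do not support that without a stated scale. It does not rescue both tables, because under the crude reading Pr(Tox.) should be near the kept column above.

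Second, Section 12.2.6 is silent on the handling, and calling the death times potential is compatible with taking whichever event comes first. That also stands. A coding error is an inference, not something the text shows.

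Third, other choices could shape Table 5. Dropping post-death DLTs and choosing only levels estimated at or below target matches Scenarios 1 to 3 about as well (distances .051/.035/.022) and brings Pr(Tox.) to .083/.055/.066/.108. It fails in Scenario 4 (0.21, against 0.08 with DLTs kept and closest-dose choice), and the documents do not state such a selection rule.

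Fourth, the rebuilds used a one-parameter model, whereas Section 12.2.1 specifies a two-parameter logistic model, which was not tested. The death times of reference 5 are also unseen.

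**Conclusion.** The point holds as an unresolved inconsistency with a conditional size. Section 12.2.6 leaves both the handling of post-death DLTs and the scale of the scenario rates unstated, and no variant tried reproduced Tables 4 and 5 together. Under those assumptions at least one of the tables misstates the design.

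If the rates are net of death, Table 5 appears to understate selection above the MTD roughly 1.5- to 3-fold in Scenarios 1, 3 and 4. If they are crude, the fault lies in Table 4's Pr(Tox.), which is about a quarter too low. A reader might infer an unconditional understatement of Table 5, or one covering all four scenarios. Neither is supported: the scale is not given, and Scenario 2 has no level above its MTD. The direction was stable over the death distributions, accrual patterns and one-parameter models tried; the exact sizes rest on assumed death times. Confidence is medium.

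**What to change.** In Section 12.2.6, state whether the scenario rates are net or crude of death and apply the matching rule. If net, a DLT occurs only when its drawn time precedes the drawn death. If crude, every drawn DLT counts, in the dose-finding and in Pr(Tox.) alike. Re-run the 5000 simulations per scenario and restate Tables 4 and 5 from that single run. Add a column for the probability that the recommended level is above the MTD, with the MTD defined on the same scale. Correct Scenario 2's 0.014.

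The cost is a re-run of existing code, a few sentences and two tables. Nothing changes for patients or procedures. The restated figures may be less favourable.

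### Tables 4 and 5 appear to describe a trial that cannot stop early, and no scenario tests the safety stop where it is meant to act

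*Combined protocol and SAP*

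**What the plan says.** Section 12.2.1 sets a TITE-CRM design "to enroll a maximum of 30 patients onto this protocol". The starting point is fixed: "The first patient in this study will enroll at dose level #2". The fitted model is to be a two-parameter logistic.

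Section 12.2.5 adds an interim safety analysis after each enrolment: "We will stop the trial early if either of the following three conditions are met". Two conditions follow: a DLT proportion above 50% at any level, and one above 34% at level 1. No third is listed. Nothing is said about a minimum number of patients at a level, or about how patients still under observation are counted.

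Section 12.2.6 describes the simulation: "We set our target rate of toxicity at the MTD to be .20", a prior given as "set a vague normal prior with mean 0 and variance 1.34", doses assigned "following the rules for dose escalation above", uniform toxicity times, death times from the literature, and 5000 runs per scenario. The stopping conditions are not mentioned. The key to Table 4 states: "Total Obs. is the cumulative observation time (in months) on all 30 patients". The most toxic scenario has "Toxicity probabilities (.05, .10, .20, .30, .50) for dose 1-5, respectively".

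**The concern.** Operating characteristics should come from the trial as it will be run. If the simulated trials could not stop, the reported 'power', duration and recommendation probabilities belong to a different procedure.

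The choice of scenarios makes this matter more. A safety stop exists for the case in which the starting level, or every level, is more toxic than expected. None of the four scenarios is of that kind, and the second stopping condition concerns level 1 alone. A review board therefore cannot see from Tables 4-5 how often the stop would act when needed, or how often the trial would finish and name a dose above the 20% target.

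**Working it through.** **Inputs from the documents.** Maximum 30 patients; target .20; start at level 2; Table 3 prior toxicities; normal prior, variance 1.34; 12-month window with proportional weights; escalation needs 12 patient-months and one patient with 6 months at the level; accrual 12 a year; toxicity times uniform over 12 months.

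**Assumed.** Death times, which the documents do not list: Weibull, median 8.25 months (the figure in 12.2.1), shape 1.5 in the main runs; other shapes changed little. A one-parameter model was used, in line with the single prior in 12.2.6.

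**1. Reproduce Table 4 with no stopping.**

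| | Stated, Scenarios 1/2/3/4 | Simulated, no stopping |
|---|---|---|
| Duration (months) | 39.4 / 39.4 / 39.5 / 39.5 | 39.4 in all four |
| Total observation (months) | 237.0 / 240.5 / 239.1 / 233.9 | 235.6 |
| Pr(Tox.) | .091 / .062 / .071 / .116 | .088 / .055 / .067 / .119 |
| 'Power' | .341 / .436 / .369 / .334 | .332 / .496 / .363 / .425 |

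Duration agrees, and total observation is within 3%. 'Power' (final dose taken as the highest with estimated DLT rate at most .20) agrees in Scenarios 1 and 3, but is off by 6 points in Scenario 2 and 9 in Scenario 4.

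**2. What stopping would do to duration.** At one patient a month, each patient not enrolled saves about one month. With the two listed conditions applied literally, mean enrolment in Scenario 4 falls to 28.4-28.8, a saving of 30 − 28.8 = 1.2 to 30 − 28.4 = 1.6 months. Expected duration is then 39.4 − 1.6 = 37.8 to 39.4 − 1.2 = 38.2. Table 4 gives 39.5.

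Simulation noise cannot hide this. If arrivals are Poisson, the SD of 29 gaps is √29 = 5.4 months, and the standard error of a mean over 5000 runs is 5.4/√5000 = 0.08. If at least three patients at a level were required, the fall from Scenario 2 to Scenario 4 is only about 0.3 months (39.3 to 39.0), so Table 4 excludes that reading less clearly.

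**3. Total observation.** It falls by 240.5 − 233.9 = 6.6 months from Scenario 2 to Scenario 4. Scenario 4 has 30 × (.116 − .062) = 1.62 more DLTs. Ending follow-up at a DLT would explain the fall at 6.6/1.62 = 4.1 months per event, so early stopping is not needed to account for it.

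**4. Table 5 row sums.** They are 1.000, 0.999, 1.001 and 1.001, with no column for stopped trials. A stopped trial could still have been assigned a dose, so this alone does not discriminate.

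**5. Scenario range.** Level 1 is .01, .01, .01, .05 and level 2 is .05, .05, .05, .10. The lowest correct MTD in any scenario is dose 3. This is exact.

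**6. Illustrative stop rates** (two listed conditions, checked at each enrolment; ranges span the survival, accrual and counting variants tried):

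| True DLT rates | Literal rule | At least 3 patients at a level |
|---|---|---|
| Scenario 1 | 5-7% | 0.3-6% across Scenarios 1-4 |
| Scenario 2 | 2-4% | |
| Scenario 3 | 3-5% | |
| Scenario 4 | 8-13% | |
| Level 1 at 25-35%, higher levels above that | 24-49% | 14-33% |

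With level 1 at 25-35%, about half or more of trials reach 30 patients and name level 1. In one set of runs at 25% the share was 66% under the literal rule and 76% with a three-patient minimum.

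With true rates (.10, .25, .35, .45, .55), where the starting level is above target, 9-19% stop. Under the literal rule, the share naming level 2 or higher was .236 + .084 + .010 + .001 = .331.

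**7. Why the reading matters.** One DLT in the only patient at a level is 1/1 = 100%, above 50%. At level 1, 1/2 = 50% exceeds 34%, but 1/3 = 33.3% does not. The stop rate therefore depends on details that 12.2.5 leaves open.

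**The case against.** No passage says that stopping was left out, and naming the escalation rules does not by itself exclude others. A reader might take the Table 5 row sums as proof; they are not. What stands is an inference from several facts, of which flat duration is the strongest.

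The simulated rule is also incomplete. A third condition is announced and absent, and it might act in exactly the untested cases. This limits every stop rate above.

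A reader might conclude that 'power' is overstated by 1-5 points. The replicates do not support a figure: those that showed such a loss gave no-stopping selection of 0.40-0.41 in Scenario 1 and 0.41-0.43 in Scenario 4, against stated values of .341 and .334. Those gaps are larger than the claimed loss.

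A reader might also conclude that the stop rarely fires when needed. Rates of 24-49% under the literal rule are not rare, and level 1 at 25% or 30% lies below the 34% threshold, so a modest rate there is what the rule implies.

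The toxic scenarios are stress tests. Table 1 gives level 1 a late-toxicity BED of 147, against 158 for the completed 6-fraction regimen and 233 for the single-fraction one, where section 1.4 reports 12/73 = 16% grade 2-4 duodenal toxicity. On the other side, the starting level has 180, above both 158 and the 106 of the 5-fraction precedent, and section 6.2 puts gastrointestinal damage above 10%. A scenario with a toxic starting level is reasonable.

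Finally, the model can de-escalate at any time and the DSMB reviews data twice a year. These are real safeguards, but neither gives the stopping rule a reported performance.

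**Conclusion.** The point holds as an inference about the simulation and as a fact about the scenarios. Tables 4-5 match a trial that always enrols 30 patients, so they probably do not describe the planned one, and the stop is not evaluated where level 1 or the starting level exceeds the target.

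In the four stated scenarios the effect is modest: about 0.3-13% of trials would stop, with a small change in correct selection that cannot be sized reliably. The larger gap is the untested case, where about 15-50% of trials would stop with level 1 at 25-35%. All these figures rest on assumed death times, a one-parameter model and a chosen reading of two conditions.

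This should be fixed, but it does not invalidate the trial. No dose assignment or stopping decision is taken from these tables.

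**What to change.** 1. Reconcile 12.2.5: state every stopping condition, whether a minimum number of patients at a level applies, and how patients with incomplete follow-up are counted. The simulation cannot be repeated faithfully until this is done.
2. Reconcile the model. Section 12.2.1 plans a two-parameter logistic, while 12.2.6 gives one normal prior. Simulate the one that will be used.
3. Re-run with the reconciled rules active, adding at least one scenario with the starting level above 20% and one with all levels above 20%.
4. Replace Tables 4-5, reporting the probability of stopping with no MTD, mean number enrolled and expected DLTs.
5. Have the sponsor and DSMB review the stopping rule against those results.

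The cost is some re-analysis and new tables, with no extra patients. The stated 'power' will probably come out slightly less favourable.
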